5-Azacitidine (AZA) and 5-aza-2'-deoxycytidine (decitabine, DAC) are pyrimidine nucleoside analogs of cytidine, both with 5' modifications of the ring. These drugs were initially used at high doses in the 1970's as cytotoxic agents, mainly in hematologic malignancies. They have since been shown to promote DNA hypomethylation at lower doses by incorporating themselves in DNA and RNA, irreversibly binding to DNA methyltransferases, and causing decreased methylation in daughter cells. This allows for reactivation of tumor suppressor genes leading to cessation of cancer cell growth, cancer cell damage and ultimately cancer cell death²⁴. In myelodysplastic syndrome and in elderly patients with acute myelogenous leukemia, AZA and DAC have demonstrated improved overall survival and time to leukemia progression²⁵⁻²⁷. A

phase III trial randomized 358 patients with high-risk MDS to receive either AZA or best supportive care. Overall survival was 24.5 months in the AZA group compared to 15.0 months in the control group²⁸. AZA and DAC are now considered the standard of care for patients with intermediate or high-risk MDS and elderly patients with AML who cannot receive high intensity treatment²⁹. As these agents work best in cells as they are diving, optimal efficacy has been seen after several months as the drugs get incorporated into the cells²⁴ and therefore are likely most effective in situations when time is available.

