While this phase III data was done using a subcutaneous administration of azacitidine, the oral formulation, CC-486, (typically given for 7-21 days and repeated every 28 day cycle) is currently being studied in early phase trials in this patient population. It was first shown to be safe at a low dose in a pilot pharmacokinetic study in 2008³⁰. In the phase I study supported by Celgene to determine the maximum tolerated dose of CC-486, 41 patients with MDS, CMML or AML refractory or inappropriate for conventional therapies received one cycle of subcutaneous azacitidine followed by cycles of CC-486 given days 1-7 of every 28 day cycle. The maximum tolerated dose (MTD) was 480 mg. The dose limiting toxicity was severe diarrhea, experienced in 2 of 3 of the patients at the 600 mg dose. Nausea, vomiting, headache, fatigue, fever, cough and febrile neutropenia were the other grade 3 adverse events observed. 8 patients were still receiving the study drug at the time of the paper's publication. CC-486 was rapidly absorbed with a mean bioavailability at the MTD of 13%. CC-486 did cause hypomethylated of a significant number of loci with peak effect at day 15 of each cycle, although not to the same extent as subcutaneous azacitidine. Clinical responses were seen in 35% of patients with MDS and CMML who were previously treated and in 73% of patients who received this as first-line therapy. Therefore, CC-486 has proved to be bioavailable, well tolerated and produce similar clinical response as the subcutaneous version³¹. This group also presented more detailed pharmacokinetic and pharmacodynamic data at the 11th International Symposium on Myelodysplastic Syndrome in Scotland in May 2011 of the above subcutaneous followed by oral dosing as well as oral dosing starting from the first cycle. This poster demonstrated data from patients who in 28 day cycles took CC-486 200 mg days 1-14, 200 mg days 1-21, 300 mg days 1-14, and 300 mg days 1-21. The 300 mg given days 1-21 of a 28 day cycle demonstrated reduced DNA methylation, provided 56% of the cumulative exposure to 5azacitidine as compared to 7 days of the subcutaneous version, and was well tolerated.

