3.4 Rationale for Treatment in this Setting

Pancreatic cancer is a highly aggressive malignancy. Increasing preclinical and clinical evidence has suggested that epigenetic therapy requires several months to achieve optimal efficacy, creating a great challenge in a rapidly progressing cancer. High-risk pancreatic cancer patients with positive nodal disease, positive resection margins, and/or elevated CA 19-9, are a unique patient population to test this type of treatment. The window of time until disease progression provides an ideal opportunity to employ epigenetic therapy. Currently, there is no consensus as to how one should treat patients with pancreatic cancer who have undergone resection and adjuvant therapy but have an elevated CA 19-9. Although CA 19-9 has a variable specificity for identifying pancreatic adenocarcinoma, its continual rise in a patient with previously known disease highly suggests microscopic recurrence, despite a lack of visible disease on scans. Physicians hesitate to give conventional cytotoxic chemotherapy in the absence of clear disease; however patients and physicians are left unsettled given the knowledge that the disease is recurring. Similarly, patients who have N1 disease or R1 resections are not typically given any further treatment after completing their adjuvant therapy in the absence of disease; however virtually all of these patients will recur. Azacitidine is a very well tolerated therapy that can be given to patients in this time period without significant toxicity. Preclinical models demonstrate that multiple tumor suppressor genes have abnormally hypermethylated promoter regions in pancreatic cancer, therefore AZA would allow for these genes to be reactivated and to slow tumor

growth. Furthermore, there is preclinical and clinical data in other solid tumors that suggests that AZA may prime the cancer to improve its response to chemotherapy – a hypothesis that our study will also test.

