11.3.4 Sample Size

The anecdotal time to progression without treatment is approximately 4 to 6 months. A feasible goal of 60 patients (30 in each arm) will provide 80% power to identify a 64% improvement in the median PFS from the null rate of 6 months assuming a one-sided type 1 error rate of 0.20, 24 months of accrual and a minimum of 12 months of follow-up while allowing for 10% loss to follow-up (protocol accruing for 6 months at the time of submission.

1-sided Type I error rate	Detectable HR (N = 60)
0.05	2.12
0.10	1.89
0.15	1.74
0.20	1.64

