11.3.6 Futility Analysis

An interim futility analysis will be performed once 50% of the expected progressions have occurred. The conditional power will be calculated for the following three scenarios for the unobserved data:

• Null hypothesis: Assumes no difference between the two treatment arms, i.e. the median PFS in both groups is 6 months.

- Alternative hypothesis: Assumes that the originally hypothesized rates (6 months vs 9.84 months) will be observed.
- Current pattern: Assumes that the PFS observed for each group in the initial cohort will be observed for the remaining patients.

The decision to stop or continue will be based upon the currently observed pattern with the null and alternative hypothesis patterns providing an estimate of the range of possible values. Since the cost of continuing (in terms of safety, resources and monetary cost) is low relative to the information to be gained, a low threshold for continuing was selected. We will stop the trial and conclude futility if the conditional power is 30% or less. Otherwise, the trial will continue. No interim efficacy analysis is planned due to the high cost of type I error spending associated with an interim efficacy analysis.

12 Regulatory Considerations

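### The 80% power ignores the futility rule, which cuts it to about 71% even with no lag; because the rule extrapolates early events, the slow onset the protocol describes makes wrongful stopping more likely

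*Combined protocol and SAP*

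**What the plan says.** On onset of effect, Section 3.3 says of azacitidine and decitabine that "optimal efficacy has been seen after several months". Section 3.4 repeats the idea: "epigenetic therapy requires several months to achieve optimal efficacy, creating a great challenge in a rapidly progressing cancer". It offers the interval before visible recurrence as the window in which such a drug can be tried.

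On power, Section 11.3.4 says the 60-patient sample "will provide 80% power to identify a 64% improvement in the median PFS from the null rate of 6 months". It assumes a one-sided type I error of 0.20, 24 months of accrual, at least 12 months of follow-up and 10% loss. The accompanying table expresses the same target as a detectable hazard ratio of 1.64. Neither a delayed effect nor the interim look is mentioned.

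On futility, Section 11.3.6 places one look at half the expected progressions and calculates conditional power for the unobserved data under the null, the alternative (6 against 9.84 months) and the current pattern. "The decision to stop or continue will be based upon the currently observed pattern"; the other two scenarios only show a range. The trial stops at conditional power of 30% or less. The same section says that continuing costs little and that a low bar for continuing was intended.

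In Section 11.3.1, PFS runs from randomisation and the arms are compared by a Cox proportional hazards model, with one-year proportions from Kaplan-Meier curves.

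**The concern.** There are two gaps. First, the 80% is the power of a design without a futility stop, but the plan commits to one. A rule that stops on the observed trend halfway through a small trial discards some trials that would have succeeded, and the stated power does not show this.

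Second, if the drug takes time to reach full effect, the events available at the interim come disproportionately from the period when the arms differ least. Projecting that pattern forward understates what the remaining events would show. The trial could then abandon a drug that achieves the target medians, for a reason its own rationale predicts.

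**Working it through.** **Inputs.** From 11.3.4: 30 per arm, medians 6 and 9.84 months, one-sided 0.20 (critical value 0.8416), 24 months of accrual, 12 months of minimum follow-up, 10% loss. From 11.3.6: look at 50% of expected events, stop at conditional power of 30% or less. Assumed: exponential PFS, uniform accrual, loss taken as 54 analysed patients (27 per arm), final analysis at 36 months, lags of 2 to 4 months.

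**1. Reproduce the 80%.** With hazard λ = ln 2 / median, P(event) = 1 − [exp(−12λ) − exp(−36λ)] / (24λ).

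- Control: λ = 0.1155, P = 0.915
- CC-486: λ = 0.0704, P = 0.793
- Events: 27 × (0.915 + 0.793) = 46.1
- Power: Φ(ln 1.64 × √(46.1/4) − 0.8416) = Φ(1.680 − 0.842) = 0.80

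Solving for the hazard ratio at each error rate gives 2.12, 1.88, 1.74 and 1.64, against the plan's 2.12, 1.89, 1.74 and 1.64. The table therefore rests on a constant ratio from randomisation and no interim stop.

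**2. Translate the futility rule.** Half of 46.1 is about 23 events; the plan gives no count. At information fraction 0.5, with B = Z√0.5, current-pattern conditional power is Φ((2B − 0.8416)/0.7071). Setting this to 0.30 gives B = 0.235 and Z = 0.333. The trial stops if the observed control-to-CC-486 hazard ratio is below exp(2 × 0.333/√23) = 1.15.

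**3. Cost with no lag.** Under the target effect, interim Z has mean ln 1.64 × √(23/4) = 1.186. P(stop) = Φ(0.333 − 1.186) = 0.20. Simulated log-rank trials give 20–21% stops and power of 70–71% once the rule is obeyed.

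**4. The same rule on the alternative scenario.** Conditional power is Φ((B + 0.5 × 1.680 − 0.8416)/0.7071). Setting it to 0.30 gives Z = −0.522, an observed ratio of 0.80.

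- Stops under the target effect: Φ(−0.522 − 1.186) = 0.04; simulated power 79%
- Stops under no effect: Φ(−0.522) = 0.30, against Φ(0.333) = 0.63 for the current-pattern rule (simulated about 31% and 64%)
- Rejection under no effect: about 19%, within the 0.20 allowed

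**5. Add a lag (simulated; ranges run from 2 to 4 months).**

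| Scenario | Final power, no look | Stopped by current rule | Power with current rule |
|---|---|---|---|
| No lag | 80% | 20% | 71% |
| Medians held at 6 and 9.84 | 79–84% | 26–31% | 65–67% |
| Gradual onset to 1.64 | 73–67% | 28–34% | 62–54% |
| Ratio 1, then 1.64 after the lag | 66–54% | 35–46% | 54–41% |

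Holding the medians despite a lag of 2, 3 or 4 months needs a post-lag hazard ratio of 1.96, 2.28 or 2.92. With a 3-month abrupt lag, about 49% of interim events fall before the drug acts, against 34% at the final analysis.

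With medians held, deciding on the alternative scenario gives 7–9% stops and 78–80% power.

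**The case against.** The strongest reply is that the documents do not describe a period without effect. Both statements concern optimal efficacy, and Section 3.3 also reports hypomethylation "with peak effect at day 15 of each cycle". This stands. The abrupt-lag row is the extreme case, and the gradual-onset row is as compatible with the text. Day 15 is a within-cycle methylation marker rather than an efficacy result, so it does not remove the question.

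A reader might infer that final power is overstated whenever there is a lag. The documents do not support that. The text of 11.3.4 defines the target as a gain in median, and if that gain is reached despite a lag, final power is kept. It falls only if 1.64 is read as the ratio after the lag.

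A reader might also infer that the futility rule assumes full effect from randomisation. It does not: the deciding scenario carries the observed pattern forward, and only the non-deciding alternative uses 6 against 9.84 months. Moving the decision to that alternative does bring in a no-lag assumption, but only for the unobserved data, and it makes wrongful stopping rarer.

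The constant control hazard may overload the early months, because entrants are free of visible disease. With an assumed rising hazard (Weibull shape 1.5–2, same median), power is 82% with no lag, 75–77% and 69–73% for abrupt lags of 2 and 3 months, and 77–79% for gradual onset over 3 months. The loss shrinks but remains.

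Finally, most of the rule's cost does not come from a lag. With medians held, a lag adds only about 6 to 11 percentage points of stops to the 20% already there. This is correct, and it is why the no-lag figure comes first.

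**Conclusion.** The point holds in this form. The stated 80% assumes a constant hazard ratio and no futility stop. With the rule in 11.3.6 applied, power is about 71% and about one in five trials with the target effect stops, with no lag at all. That result needs only the plan's own inputs plus the assumptions of exponential PFS, a look at about 23 events and a final test at one-sided 0.20.

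The slow onset described in Sections 3.3 and 3.4 raises the stop probability in every scenario examined, to between 26% and 46% for lags of 2 to 4 months. The direction is firm. The size is an assumed range, because the protocol does not quantify the lag. A stop rate of 20% or more under the target effect sits poorly with the plan's own view that continuing is cheap.

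**What to change.** 1. **Section 11.3.4.** State that 80% assumes a constant effect from randomisation and no futility stop. Add power with the rule applied (about 71% with no lag) and a sensitivity range for lags of 2 to 4 months, separating the case where the medians are held from the case where 1.64 applies only after the lag.
2. **Section 11.3.6.** State the event count for the look. Base the stop on the alternative-scenario conditional power already calculated, keep the 30% threshold, and report the current-pattern value as supportive. If the sponsor prefers the present rule, keep it and restate the power.
3. **Section 11.3.1 (optional).** Add a 12-month restricted mean PFS difference as supportive, beside the one-year PFS proportions already planned. The Cox comparison stays primary. Do not split the hazard ratio at 3 months: the cut would fall on the first scheduled scan, and scan timing in Arm B is discretionary.

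The cost is wording only, with no extra patients. The real trade-off is in item 2: if the drug has no effect, the chance of stopping early falls from about 64% to 31%, so more ineffective trials would run to completion. Rejection under no effect stays at about 19%.

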3.3.1 Indication and Usage

5-Azacitidine is indicated for treatment of patients with both low and high-risk myelodysplastic syndrome (MDS) for the following French-American-British (FAB) subtypes: refractory anemia (RA) or refractory anemia with ringed sideroblasts (RARS) (if accompanied by neutropenia or thrombocytopenia or requiring transfusions), refractory anemia with excess blasts (RAEB), refractory anemia with excess blasts in transformation (RAEB-T), and chronic myelomonocytic leukemia (CMMoL). It is also considered a category 2B recommendation per the NCCN guidelines (based on lower-level evidence with a non-uniform NCCN consensus but no major disagreement) for elderly patients with AML who cannot receive conventional high-intensity chemotherapy.

3.3.2 Adverse Events

The most common adverse reactions (>30%) for the subcutaneous route per the package insert are: nausea, anemia, thrombocytopenia, vomiting, pyrexia, leukopenia, diarrhea, injection site erythema, constipation, neutropenia and ecchymosis. The most common adverse reactions by IV route also include petechiae, rigors, weakness and hypokalemia.

The most common adverse reactions for the oral route (CC-486) per the phase I trial were: diarrhea, nausea, constipation, vomiting, abdominal pain, headache, fatigue, peripheral edema, fever, cough, confusion, dizziness and febrile neutropenia. The DLT was diarrhea³¹.

Complete and updated adverse events are available in the Investigational Drug Brochure and the IND Safety Letters.

3.4 Rationale for Treatment in this Setting

Pancreatic cancer is a highly aggressive malignancy. Increasing preclinical and clinical evidence has suggested that epigenetic therapy requires several months to achieve optimal efficacy, creating a great challenge in a rapidly progressing cancer. High-risk pancreatic cancer patients with positive nodal disease, positive resection margins, and/or elevated CA 19-9, are a unique patient population to test this type of treatment. The window of time until disease progression provides an ideal opportunity to employ epigenetic therapy. Currently, there is no consensus as to how one should treat patients with pancreatic cancer who have undergone resection and adjuvant therapy but have an elevated CA 19-9. Although CA 19-9 has a variable specificity for identifying pancreatic adenocarcinoma, its continual rise in a patient with previously known disease highly suggests microscopic recurrence, despite a lack of visible disease on scans. Physicians hesitate to give conventional cytotoxic chemotherapy in the absence of clear disease; however patients and physicians are left unsettled given the knowledge that the disease is recurring. Similarly, patients who have N1 disease or R1 resections are not typically given any further treatment after completing their adjuvant therapy in the absence of disease; however virtually all of these patients will recur. Azacitidine is a very well tolerated therapy that can be given to patients in this time period without significant toxicity. Preclinical models demonstrate that multiple tumor suppressor genes have abnormally hypermethylated promoter regions in pancreatic cancer, therefore AZA would allow for these genes to be reactivated and to slow tumor

growth. Furthermore, there is preclinical and clinical data in other solid tumors that suggests that AZA may prime the cancer to improve its response to chemotherapy – a hypothesis that our study will also test.

3.5 Correlative Studies

Correlative studies will be performed to determine if therapy with CC-486 results in demethylation which can be detected in tumor tissues, as well as plasma. These studies will also evaluate for an epigenetic signature that can help predict patients who will be responders versus non-responders and identify predictive signatures of possible recurrence and benefits of CC-486 therapy.

Blood for correlative studies will be drawn from both Arm A and Arm B patients at screening and/or on Day 1 of Cycle 1. Patients in Arm A will have research blood work done on Cycle 1 Day 1 if Day 1 is not within 7 days of screening, and Day 1 of every subsequent cycle.

For patients in Arm B, additional research blood work is optional, except for at visible disease progression. If patients in Arm B choose to provide research blood, it will be collected every third cycle beginning at Cycle 4. Research blood will be collected at recurrence if it was not collected within the last three months.

These correlative studies are done in order to evaluate the methylation status of free tumor DNA circulating in the blood. Quantitative analysis using real-time Methylation-specific PCR (MSP) will be used to detect the presence of methylated alleles for specific genes. Candidate genes found to be hypermethylated in pre-treatment samples will be monitored for changes in methylation during and after treatment using real-time MSP. Methylation status analysis will also be done on pre-treatment and post-treatment samples using a novel nano-enabled methylation based technology, Methylation-on-Beads. This assay has shown great promise as a tool for surveillance of responses to epigenetic therapy. Blood will also be stored to use in the future if new biomarkers are developed that may better predict recurrence.

All patients will also undergo a tumor biopsy at the time of their recurrence on scans that will be examined with their original resected pancreatic tumor. All biopsy specimens will undergo tumor methylation analysis with MSP for select candidate genes (*TMS1*, *ARH1*, etc). Where sufficient tissue is obtained, samples will also be studied using HumanMethylation 450K BeadChip (Illumina). This technology examines over 450,000 CpGs and we will analyze the data and integrate the methylome data with mRNA or miRNA expression array studies.

4 Study Objectives and Endpoints

4.1 Objectives

Primary objective:

To improve progression free survival in patients with resected pancreatic adenocarcinoma who have node positive disease, margin positive disease, and/or elevation in CA 19-9 treated with CC-486 as compared to observation after completion of adjuvant therapy.

Secondary objectives:

- 1) To improve response rates to first line chemotherapy (partial and complete response) after recurrence in patients treated with CC-486 after completing adjuvant therapy
- **2)** To improve overall survival in patients with resected pancreatic adenocarcinoma treated with CC-486.
- **3)** To evaluate resected pancreatic cancer tissue and biopsies at time of recurrence for epigenetic and genetic alterations to determine the pharmacodynamic effects of CC-486.
- **4)** To evaluate resected pancreatic cancer tissue and blood samples to identify predictive signatures of possible recurrence and the benefit of hypomethylating therapy.
- 5) To evaluate quality of life on CC-486 using the FACIT-Hep questionnaire

4.2 Endpoints

Primary endpoint

The primary endpoint of the trial is to demonstrate an increase in the progression free survival, PFS, in resected pancreatic cancer patients treated with CC-486

Secondary endpoints

- 1) Response rate (including partial and complete response) to first line chemotherapy when given after visible disease recurrence in patients primed with CC-486 compared to observation
- 2) Overall survival
- **3)** Decreased methylation in candidate genes in the research biopsies as compared to the original resected specimens in patients treated with CC-486.
- 4) Change in quality of life scores as determined by FACIT-Hep

5 Investigational Plan

[figure not shown]
5.1 Overall design

This is a randomized, phase II study of CC-486 versus observation in patients with resected pancreatic adenocarcinoma who have finished adjuvant chemotherapy and/or chemoradiation (or were deemed unable to receive adjuvant therapy) with no evidence of visible disease on imaging and have high risk features. High risk features are defined as an elevated CA 19-9 level > ULN drawn on 2 occasions at least 2 weeks apart; positive nodal disease; and/or positive resection margins. The study will be conducted at Johns Hopkins University, The University of Pennsylvania, Massachusetts General Hospital, and Beth Israel Deaconess Medical Center. Patients will be randomized to one of two arms to enable us to evaluate for effects of CC-486 in this population. Arm A will be started on CC-486 at 300 mg daily for 21 days, repeated every 28 day cycle. The maximum tolerated dose from the phase I trial in patients with MDS, CMML and AML was 480 mg given for 7 days every cycle³¹, however this lower dose given for a prolonged period of time appeared to be tolerated better and had good bioavailability. Arm B will receive observation only. It will be recommended that patients obtain a CA 19-9 and tumor assessment every three months, however, schedule variations are permitted at the oncologist's discretion. Patients on the observation arm who are unable to travel to study site may be followed by their local oncologist ideally adhering to the same schedule. When patients have visible disease recurrence on CT scan, Arm A will stop the CC-486 and may begin their preferred cancer treatment regime. Similarly, after visible recurrence on imaging, Arm B will begin their preferred cancer treatment regime. Both Arm A and Arm B patients will follow the Follow-up schedule after their first visible disease progression. Once patients have had a 2nd instance of visible disease progression, they will be moved to the survival follow-up schedule. We will power this study in order to see a 64% increase of the progression free survival between the two groups. This will require approximately 60 patients to be enrolled and randomized.

5.1.1 5-Azacitidine Description

5-Azacitidine is a pyrimidine nucleoside analog of cytidine. 5-Azacitidine is 4-amino-1- β -Dribofuranosyl-s-triazin-2(1H)-one. The empirical formula is C₈H₁₂N₄O₅. The molecular weight is 244. The structural formula is:

Chemical Structure of 5-Azacitidine

5-Azacitidine is a white to off-white solid. It was found to be insoluble in acetone, ethanol, and methyl ethyl ketone; slightly soluble in ethanol/water (50/50), propylene glycol, and polyethylene glycol; sparingly soluble in water, water saturated octanol, 5% dextrose in water, N-methyl-2-pyrrolidone, normal saline and 5% Tween 80 in water; and soluble in dimethylsulfoxide (DMSO).

